- N: Methaemoglobin: Screening single measurement. Days 1, 8 and 14: continuous measurement for an hour ± 10 mins from start of treatment on the first dose of that day only.
- O: β -HCG Serum Pregnancy Test: All female participants (section 4.3.4).

2. Introduction

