2.2.2.3. Nonclinical Safety Pharmacology

The safety pharmacology of NO has been well characterised in the literature. This includes effects on the cardiovascular system, respiratory system, central nervous system and blood oxygenation (Table 6).

Table 6: Publications Demonstrating Nitric Oxide Nonclinical Pharmacology

Finding/s	Publication
Cardiovascular: Nitrites cause vasodilation thereby reducing BP by a cyclic guanosine monophosphate-mediated mechanism. A compensatory increase in HR has been seen in the dog with shortened PR and QT intervals. However, this occurred in a dose dependent manner and the corresponding human equivalent doses are substantially more than those proposed clinically. The morphology of the ECG as well as quantitative measurement of the corrected QT intervals and QRS complex duration in dogs were not affected. Tolerance or increased sensitivity to the effects on BP and HR was not observed.	(Bryan NS, 2015) (Rubin LJ, 2006) (Tepper J, 2014)
Respiratory: In dogs and rats there were no adverse respiratory effects.	(Tepper J, 2014)
Central Nervous System: Effects on the CNS were not identified following oral administration of sodium nitrite or inhalation of sodium nitrite or nitric oxide gas.	(Calabrese, 2007)
Blood oxygenation: Dogs given a single dose displayed increased respiration, HR, ECG changes and methaemoglobinaemia within 1 to 2 hours of administration. This however, occurred in a dose dependent manner.	(WHO, 1996)

BP: Blood Pressure, CNS: Central Nervous System, ECG: electrocardiogram, HR: Heart Rate

The observed effects, documented in these publications, on the cardiovascular, central nervous systems (if any) along with the potential for development of methaemoglobinaemia all occurred at doses in excess of those proposed clinically. Hence, the potential for development of methaemoglobinaemia and effects on the cardiovascular, respiratory, and central nervous systems following the proposed use of RESP301 are considered to be low.

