2.2.3.2. Inhaled Sodium Nitrite Published Literature

Inhaled sodium nitrite, formulated similarly to RESP301, has been assessed during inhalation studies in man and was well tolerated based on clinical studies obtained from published literature. (Rix PJ, 2015) (Borlaug BA, 2016) (Parakaw T, 2017). Key points are noted in Table 10 with more detail in the IB and references.

To support its use, safety reviews for both sodium nitrite and nitric oxide by the inhaled and/or oral route have been performed by regulatory agencies from the chemical, occupational and food safety industries e.g., ECHA, EFSA and NIOSH.

Table 10: Key Points* of Inhaled Nebulised Sodium Nitrite Clinical Data from Literature

Summary	Relevant Results	Reference
The pharmacokinetics, pharmacodynamics, and tolerability of nebulized sodium nitrite (AIR001) following single and repeated inhalation were assessed in three individual studies, in which a total of 82 healthy male and female subjects were treated.	Pulmonary absorption of nitrite was rapid and complete, and plasma exposure dose was proportional through the MTD dosage level of 90 mg, without accumulation following repeated inhalation. At higher dosage levels, DLTs were orthostasis (observed at 120 mg) and hypotension with tachycardia (at 176 mg), but venous methaemoglobin did not exceed 3.0 % at any time in any subject. Neither the tolerability nor pharmacokinetics of nitrite was impacted by conditions of mild hypoxia, or co-administration with sildenafil.	(Rix PJ, 2015)
Double-blind, randomized, placebo-controlled, parallel-group study designed to study the effects of nebulised inhaled sodium nitrite on cardiovascular haemodynamics at rest and during exercise in subjects with heart failure with preserved ejection fraction.	The inhaled nitrite was well tolerated. No subject developed hypotension, cough, and bronchospasm or reported headache or other adverse effects after inhalation of nitrite. No subject developed clinically meaningful methaemoglobinaemia. Nitrite (NO ₂ ⁻) levels increased to 11.1±4.9 µmol/L in subjects receiving active drug (p<0.0001 vs baseline). The calculated half-life of nitrite in this study was 0.72±0.74 hours.	(Borlaug BA, 2016)

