5.3.2. Dosing Instructions

The methodology will be detailed in the Pharmacy Manual.

On the days of IMP dosing:

Inhaled RESP301 nebulisation:

- all treatment regimens:
 - each dose is to be given using freshly prepared admix solution i.e., inhalation of the RESP301 should start with [REDACTED]
 - on Day 1 only: a short acting beta agonist is to be administered before starting the nebulisation for each dose, within 30 minutes of RESP301 is suggested
 - inhalation of RESP301 should be completed within [REDACTED] of starting NEB, pauses may be taken during NEB if not tolerated. The NEB should be stopped during a pause to preserve the remaining IMP until restarted.
 - the first dose should be given in the morning
 - All dosing should occur at approximately the same time each day (window of \pm 1 hour of the IMP dose/s on Day 1).
- once or twice daily:
 - When dosing overlaps with overnight sputum sample collection, sputum collection should be paused during and for [REDACTED] the end of the neb. A cup ([REDACTED] [REDACTED]) of water should be taken after the neb is complete, and prior to continuation of overnight sputum sample to wash away any remaining RESP301 from the airway.
 - the first dose should be given at half dose (half of each vial)
- three times a day (alone or with HRZE):
 - the first 2 doses should be given at half dose (half of each vial)
 - this tds dosing will be [REDACTED] to prevent overnight disruption to participants and limit overlap of dosing and sputum sampling
- twice or three times a day (alone or with HRZE):
 - to ensure a dose does not affect any *M.tb* present in the overnight sputum sample, should a dose overlap with the overnight sample collection window, sputum collection is

to be paused for [REDACTED] completion of inhalation of the RESP301 dose. Should the participant need to expectorate sputum during this pause, this will occur into a separate container which will be destroyed. The participant is to drink a cup ([REDACTED]) of water after the neb is complete, and prior to continuation of overnight sputum sample collection

HRZE oral dosing (alone or with RESP301):

- to occur in the morning
- preferably with a full glass of water fasted [REDACTED] However, if gastrointestinal irritation occurs, the tablets may be taken with food.
- if aluminium containing antacids are taken, administer one hour after the HRZE tablet/s dose.

HRZE plus RESP301 three times a day

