- RESP301 tds instructions and the HRZE instructions above to apply.
- oral dose of the HRZE should be given in the morning, followed within [REDACTED] the start of the first (morning) dose of inhaled RESP301.

The exact dosing times (start time and end time) of each individual IMP will be recorded.

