7.10.2. Methaemoglobinaemia

If a Grade 2 or higher (CTCAE grading) level of Methaemoglobinaemia is observed following administration of IMP, the IMP should be discontinued immediately and continuous transcutaneous monitoring instituted until Methaemoglobin levels have fallen to 1.5%. No active treatment is required and withdrawal of the patient from the study is at the discretion of the investigator. Subsequent administration of the IMP should be accompanied by transcutaneous MetHb monitoring which should be continued for 60 minutes after the end of administration.

If a grade 3 or higher (CTCAE grading) Methaemoglobinaemia occurs with IMP dosing, the IMP should be discontinued immediately. The patient should be monitored, and standard supportive medical treatment should be applied as required.

CTCAE Term	Grade 1	Grade 2	Grade 3	Grade 4	Grade 5
Methaemoglobinaemia	-	>ULN 5% sustained for more than 1-minute transcutaneous measurement	Requiring urgent intervention >10%	Life-threatening consequences >40%	Death (>70%)

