##### Methemoglobin

The assessment of Methemoglobin using Spmet will be summarized by single SpMet measurement and Highest SpMet measurement per treatment and time of assessment using descriptive statistics.

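### The recorded SpMet hour starts with treatment, so post-dose observation shrinks as nebulisation lengthens and the highest SpMet may understate the peak

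*Protocol*

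**What the plan says.** Protocol 1.3 (Study Flow Chart, note N) sets one SpMet measurement at screening and, on Days 1, 8 and 14, "continuous measurement for an hour ± 10 mins from start of treatment on the first dose of that day only".

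Protocol 5.3.2 (Dosing Instructions) says that "pauses may be taken during NEB if not tolerated", with the nebuliser switched off meanwhile. The limit for completing the inhalation is redacted. In the combination arm the "oral dose of the HRZE should be given in the morning, followed within" a redacted interval by the first RESP301 dose. Section 5.3.3 has staff monitor SpMet while each dose is being nebulised, and start and stop times of inhalation are recorded.

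Protocol 7.10.2 (Methaemoglobinaemia) uses another time origin. After a Grade 2 or higher event, it says: "Subsequent administration of the IMP should be accompanied by transcutaneous MetHb monitoring which should be continued for 60 minutes after the end of administration".

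SAP 10.2.3 (Methemoglobin) has SpMet "summarized by single SpMet measurement and Highest SpMet measurement per treatment and time of assessment", with descriptive statistics. The dataset table in SAP 7.1 likewise holds the highest SpMet value. Neither place states the window over which the highest value is taken. Methaemoglobin is one of the secondary safety measures in Protocol 1.2.

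**The concern.** The recording has a fixed length from the start of dosing, but what matters for a maximum is how long the participant is observed once the dose is in. That time differs between participants and depends on tolerance: a participant who pauses receives the dose later and is then observed for less time.

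Because the analysed variable is a maximum, the error can go only one way. If SpMet is still rising when recording ends, the summary is too low, and most so in the participants of greatest interest for safety. In the combination arm, note N does not say which product starts the hour. HRZE is also study treatment and is given first, so a literal reading could start the hour before RESP301.

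**Working it through.** **Step 1. Window arithmetic (no kinetic assumption).** Let W be the recording length from the start: 60 minutes, or 50 to 70 with the tolerance in note N. Let D be the time from start to end of nebulisation, pauses included. D is redacted, so 10 to 40 minutes is assumed. Recorded post-dose time = W − D.

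| D (min) | W = 60 | W = 50 to 70 |
|---|---|---|
| 10 | 50 | 40 to 60 |
| 20 | 40 | 30 to 50 |
| 30 | 30 | 20 to 40 |
| 40 | 20 | 10 to 30 |

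A 20-minute nebulisation with 20 minutes of pauses has D = 40, and its post-dose recording falls from 40 to 20 minutes.

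**Step 2. What the documents say about timing.** None of this is a time to peak methaemoglobin for RESP301.

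- Protocol Table 6 reports "methaemoglobinaemia within 1 to 2 hours of administration" in dogs, among other signs. The route is not stated and no peak time is given.
- Protocol 2.2.2.5 puts the rat plasma nitrite peak at the end of inhalation. That is nitrite, not methaemoglobin.
- The same section describes rapid oxidation of NO-bound haemoglobin to methaemoglobin after inhaled NO, which could give an earlier component.
- Protocol Table 10, on inhaled sodium nitrite in heart failure: "The calculated half-life of nitrite in this study was 0.72±0.74 hours".

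**Step 3. Illustrative size.** The model has constant nitrite input over D, first-order nitrite loss (rate kN), methaemoglobin formed in proportion to that loss, and first-order recovery (rate kM), with k = ln 2 / half-life. For t ≥ D, up to a constant that cancels:

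M(t) = kN / [D(kM − kN)] × { [e^(−kN(t−D)) − e^(−kN·t)]/kN − [e^(−kM(t−D)) − e^(−kM·t)]/kM }

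Capture = highest M within the window ÷ overall highest M. The nitrite half-life is 0.72 h (43.2 min, from the document); the recovery half-life is assumed.

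Example: D = 40, recovery half-life 2 h, so kN = 0.01605 and kM = 0.00578 per minute. M(60) = 0.406, M(100) = 0.546, and the peak is M(121) = 0.559. Capture at 60 min from start = 0.406/0.559 = 73%. At 60 min from the end it is 0.546/0.559 = 98%.

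Capture (%) at 60 min from start:

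| Recovery half-life | D = 10 | D = 20 | D = 30 | D = 40 |
|---|---|---|---|---|
| 15 min | 100.0 | 100.0 | 100.0 | 100.0 |
| 30 min | 100.0 | 99.9 | 98.6 | 95.5 |
| 1 h | 96.3 | 93.6 | 89.6 | 84.3 |
| 2 h | 87.1 | 83.2 | 78.4 | 72.6 |
| 3 h | 81.6 | 77.5 | 72.6 | 66.9 |

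For recovery half-lives of 1 to 3 h:

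- The peak falls 78 to 138 min after the start.
- Capture is 67% to 96% at 60 min from start, and 55% to 90% at 50 min.
- For comparison, 60 min counted from the end gives 88% to 100%.

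**Step 4. Sensitivity to the nitrite half-life.** The source figure has an SD larger than its mean. With 20 min instead of 43 min, capture at 60 min from start is 88% to 100% for recovery of 1 to 3 h, and 100% for recovery of 15 to 30 min. One SD above the mean (1.46 h, about 88 min) lowers it: 54% for D = 30 and recovery of 3 h.

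**The case against.** The strongest reply has four parts.

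1. A reader might take note N and 7.10.2 as contradictory. They are not. The 7.10.2 clock applies only to later doses after a Grade 2 or higher event, and closer observation after an event can reasonably differ from routine recording. This stands. What remains is an unexplained difference in time origin.

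2. A reader might infer that the methaemoglobin results will understate the peak. The documents do not show this. If methaemoglobin peaked at the end of inhalation, nothing would be lost unless nebulisation outlasted the window. The model leaves out methaemoglobin formed directly from inhaled NO and relies on a redacted duration and an assumed recovery half-life. This stands, and it limits the claim to a possible understatement.

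3. There is partial cover elsewhere. SpMet is watched during every nebulisation, and after a Grade 2 reading monitoring continues until the level has fallen, so a high value seen within the hour is not cut off. Table 20, which lists the safety assessments, is redacted and may say more. This also stands, but in the visible text nothing extends the recording for a participant whose level is still below Grade 2 and rising when the hour ends.

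4. A reader might infer a biased comparison between arms, chiefly against the combination arm. That needs a literal reading of note N and a redacted HRZE-to-RESP301 interval, and the SAP plans only descriptive summaries. It is not supported beyond a need to clarify which product starts the hour.

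None of this touches Step 1: post-dose observation varies with nebulisation time and is shortened by pauses for intolerance.

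**Conclusion.** The concern holds as a measurement weakness. Post-dose SpMet recording equals 60 minutes (± 10) minus nebulisation time, so it is 50 minutes for a 10-minute nebulisation and 20 minutes for a 40-minute one. It is shortest relative to the end of dosing in participants who pause, although the recording closes at the same time from start for everyone. A maximum taken over such a window may understate the peak and cannot overstate it.

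The size is uncertain. Illustrative capture at 60 minutes from start is about 67% to 100% for 10 to 40 minutes of nebulisation, with a nitrite half-life of 0.72 h or 20 min and recovery half-lives from 15 min to 3 h. The lower figure is not a bound, since a longer nitrite half-life would reduce it, and the upper end is no loss at all. The documents cannot settle where RESP301 lies. This is a worthwhile, cheap improvement and not evidence that the safety results will be wrong.

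**What to change.** The changes concern the recorded endpoint only; no monitoring threshold or clinical action is proposed.

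- Note N: reconcile its time origin with 7.10.2. Define the recorded window relative to the end of RESP301 nebulisation, keeping the readings taken during it, so that post-dose observation is the same for all. The sponsor sets the length and justifies it against whatever time-to-peak data it holds.
- Note N: state that treatment means RESP301 in the combination arm. The HRZE-only arm has no nebulisation and needs its own stated origin.
- SAP 10.2.3: define the highest SpMet as the maximum over that window.

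The cost is a few sentences. If the post-dose length stays at about an hour, the monitor stays on for roughly the nebulisation time longer on three mornings. Dose start and stop times are already collected, so no new dosing-time data are needed.

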2.1. Background Information

2.1.1. Tuberculosis

Tuberculosis (TB), caused by *Mycobacterium tuberculosis* (*M.tb*) infection, remains a concerning global health problem. TB is present in all countries and age groups. In South Africa, the estimated burden of bacteriologically confirmed pulmonary TB among people aged 15 years or older in 2017–19 was 852 cases per 100 000 population. (Moyo S, 2022 Aug) Worldwide a total of 1.6 million people died from TB in 2021, with TB the 13th leading cause of death and the second leading infectious killer after COVID-19 (above HIV/AIDS). Eight countries in Africa and Asia accounted for more than two thirds of the global TB cases reported in 2021, with an estimated 10.6 million people falling ill with TB worldwide. However, the COVID-19 pandemic had a damaging impact on access to TB diagnosis and treatment and the burden of TB disease. The most obvious and immediate impact was a large global drop in the reported number of people newly diagnosed with TB. Reductions in the reported number of people diagnosed with TB in 2020 and 2021 suggest that the number of people with undiagnosed and untreated TB has grown, resulting first in an increased number of TB deaths and more community transmission of infection and then, with some lag-time, increased numbers of people developing TB. The burden of drug-resistant TB (DR-TB) is also estimated to have increased between 2020 and 2021, with 450 000 new cases of rifampicin-resistant TB (RR-TB) in 2021. (WHO, 2022). Whilst official numbers have yet to be published, it is accepted in scientific circles that TB is once again the leading cause of death due to infectious disease.

Whilst drug-sensitive (DS)-TB is a treatable and curable disease, it is treated with a standard 4-month or 6-month course of four antimicrobial drugs. For this treatment to be effective and not lead to an increased likelihood of developing drug-resistance, adherence is essential. (WHO, 2022) However, the duration of treatment plus the treatment side effects often does result in poor adherence. Overall, the current long-standing first-line antituberculosis agents are relatively ineffective in controlling the TB epidemic, especially in high-burden countries.

Drug-resistant (DR)-TB also poses a major threat to the control of the TB epidemic. Strains that are resistant to one or more of the standard TB treatments have been documented in every country surveyed by the WHO, who note that multidrug resistant (MDR)-TB, resistance to rifampicin and isoniazid, remains a public health crisis and a health security threat. Globally, there were an estimated 450 000 incident cases of MDR/Rifampicin resistant (RR)-TB in 2021, up 3.1% from 437 000 in 2020. An estimated 191 000 deaths occurred due to MDR/RR-TB in 2021. Globally in 2021, the estimated proportion of MDR/RR-TB cases with even more extensive resistance, was 20%. (WHO, 2022)

Significant progress has been made in recent years in identifying more efficacious, safer medicines and shorter treatment regimens. However current treatment regimens for MDR/RR-TB patients are far from satisfactory. Compared with treatments for DS-TB, these regimens require a longer course of treatment (minimum 6 months), a higher pill burden, and the use of medicines with a higher toxicity profile. In addition, patients may develop significant adverse events and have poorer treatment outcomes. Globally, although treatment success rates have increased, almost 15% of patients with MDR/RR-TB or more advanced forms of DR-TB die from the disease. (WHO, 2022).

2.1.2. Early Bactericidal Activity Clinical Studies

Achieving clinical proof of concept (PoC) for a new drug represents a major achievement and triggers significant investment into its further clinical development. It also results in parallel optimisation of production of the active pharmaceutical ingredient (API) and drug product. In TB, the assessment of the early bactericidal activity (EBA) of antituberculosis agents in sputum over the first few days up to 2 weeks of treatment is the established method for the early clinical evaluation of new antituberculosis agents and regimens. (EMA, 2017) (FDA, 2022) (Jindani A, 1980) The primary endpoint of EBA studies is the daily rate of change of colony forming units (CFU) of *M.tb* in sputum (measured as \log_{10} CFU/mL sputum/day) or the prolongation of time to positivity (TTP) in liquid culture (measured in hours/day) in patients with newly diagnosed smear-positive pulmonary TB. (Diacon AH, 2014) The latter provides an indication whether a novel treatment has antituberculosis properties in humans and gives an early indication of the dosage required. Pharmacokinetic analyses offer the opportunity to study the relationship between dose, drug concentrations and between-participant variabilities due to covariates such as age, bodyweight, renal function etc. Preliminary safety and tolerability data can also be collected for the duration of the treatment. (Diacon A, 2011; Donald PR, 2003)

2.2. RESP301

Refer to the Investigator Brochure (IB) for full information.

2.2.1. Mechanism of Action

Nitric Oxide (NO) is produced by many cells in the human body and is an important physiological first line of defence against a range of pathogens including bacteria, viruses, fungi, and yeasts. (Fang FC, 1997) (Schairer DO, 2012) (Kao YJ, 2001) The physiological role of NO and the enzymatic pathway for its synthesis via NO synthase have been clearly established for many years. (Moncada S, 1999 Apr) An alternative non-enzymatic synthetic pathway for NO synthesis is used in the human entero-salivary system and involves the acidification of dietary nitrates and nitrites to form nitric oxide in the stomach.

[REDACTED]

[REDACTED]

RESP301 is a nitric oxide generating solution. [REDACTED]

[REDACTED]

[REDACTED]

[REDACTED]

[REDACTED]

[REDACTED]

[REDACTED]

[REDACTED]

As a powerful antimicrobial agent, NO has both a direct antimicrobial action and an important role in initiating the innate immune response to infection (Bogdan C, 2015) in the lungs. (Bogdan C, 2001) The mode of action is determined by NO concentration, cell type, and local context.

At high concentrations in the micromolar range ($\geq 1 \mu M$) and above, NO:

- directly impairs bacterial enzyme activity by irreversibly binding iron sulphur cluster residues and inhibit cellular respiration by binding heme groups within cytochrome oxidases. (Wink DA, 1998) (Thomas DD, 2008) (Radi R, 2018)
- reacts with oxygen and superoxide spontaneously to generate further species that can cause protein damage, through thiol and tyrosine nitrosylation, DNA damage through base deamination, and damage to membranes and lipid structures through lipid peroxidation. (Hogg N, 1999) (Toledo JC, 2012)

At low concentrations in the nanomolar range ($\leq 1 \mu M$), NO regulates and can promote the growth and activity of immune cells by e.g., guanylate cyclase activation. (Tripathi P, 2007) (Schairer DO, 2012)

NO is thus an integral, highly conserved, part of the host immune response, with very limited evidence of bacterial resistance to its antimicrobial effect. (Andreakis N, 2011) (Joerink M, 2006) (Privett BJ, 2012)

Inhaled Nitric Oxide gas is already marketed as a therapeutic agent in the US (INOmax) where it is indicated to improve oxygenation in neonates with hypoxic respiratory failure. (FDA, 2015)

[REDACTED]

[REDACTED]

